#### 6.2.2. Haematology and clinical chemistry

Due to the location of the study sites, the transit time required for shipment of samples and logistical constraints of cold-chain storage, haematology and clinical chemistry tests will be conducted by local laboratories for this study, rather than a central laboratory.

Clinical chemistry blood samples will be taken on days 0 (pre-dose), 3, 7 and 42. Samples should only be taken on day 14 or 28 if the previous results were abnormal. Clinical chemistry tests may be performed at the physician's discretion at any time on unscheduled follow-up visits.

Clinical chemistry tests to include: serum creatinine, serum total and indirect bilirubin, serum aspartate aminotransferase (AST) and serum alanine aminotransferase (ALT).

Haematology blood samples will be taken on days 0 (screening), 1, 2, 3, 7, 14, 28 and 42. Samples taken on days 0, 1 and 2 should be taken **before** dosing. Haematology tests may be performed at the physician's discretion at any time on unscheduled follow-up visits. Haematology tests to include: haemoglobin, haematocrit, reticulocyte count (% of red blood cells and absolute count calculated against red blood cells), red blood cell count, white blood cell count, platelet count, methaemoglobin when available.

#### 6.2.3. G6PD analysis

Two drops of blood will be collected onto pre-printed filter papers on day 0, prior to administration of the first dose of study medication, for subsequent DNA extraction and PCR of the subject's G6PD gene. Loci of interest in the G6PD A- deficient variant most commonly found in sub-Sahara Africa are: 202A,376G; 376G,680A and 376G,968C. The Santamaria variant (376G,542T) is also found in the extreme West Africa and in The Gambia.

An aliquot of the day 0 haematology whole blood sample will be used to test for G6PD deficiency using the NADPH fluorescence method. Blood may be stored at 4°C for up to one week prior to analysis. A commercially available test will be used, run against standard controls (G6PD normal, G6PD deficient and G6PD intermediate). Filter papers

will be stored at 4°C in the dark until analysis, see Study Reference Manual for more detail.

A repeat phenotype test will be conducted at day 28 on any subject who experiences a fall in haemoglobin of  $\geq$ 40% from baseline during the study, or if their day 0 reticulocyte count was high.

#### 6.2.4. Pregnancy

Female subjects of child-bearing potential, defined as aged  $\geq 12$  years will be asked to take a serum pregnancy test prior to enrolment into the study. They will be asked to take a urine pregnancy test on day 42 or on early withdrawal from study.

Female subjects of child-bearing potential, as defined as aged  $\geq 12$  years, and sexually active should use barrier contraceptive measures for the duration of the study period. Condoms and spermicide will be provided by the investigator / study team, and appropriate counselling should be given to female subjects of child-bearing potential about the risks of becoming pregnant and exposing the foetus to study drugs during the consent process. See Study Reference Manual for further details.

#### 6.2.4.1. Time period for collecting pregnancy information

Pregnancies will be reported from the time of the first dose to the end of follow-up (day 42, unless the subject is withdrawn earlier).

#### 6.2.4.2. Action to be taken if pregnancy occurs

The investigator will collect pregnancy information on any female subject, who becomes pregnant while participating in this study. The investigator will record pregnancy information on the appropriate form and submit it to GSK within 2 weeks of learning of a subject's pregnancy. The subject will also be followed to determine the outcome of the pregnancy. Information on the status of the mother and child will be forwarded to GSK. Generally, follow-up will be no longer than 6 to 8 weeks following the estimated delivery date. Any premature termination of the pregnancy will be reported.

While pregnancy itself is not considered to be an AE or SAE, any pregnancy complication or elective termination of a pregnancy for medical reasons will be recorded as an AE or SAE (see AE/SAE section of the protocol and the SRM for definitions and a description of follow-up).

A spontaneous abortion is always considered to be an SAE and will be reported as such. Furthermore, any SAE occurring as a result of a post-study pregnancy and is considered reasonably related to the investigational product by the investigator, will be reported to GSK as described in section entitled, "Post-study AEs and SAEs" of the SRM. While the investigator is not obligated to actively seek this information in former study participants, he or she may learn of an SAE through spontaneous reporting.

#### 6.2.5. Home visits

A field-worker should make a home visit to all study participants on days 4, 5 and 6 to ensure that the subject is well enough to remain at home. If any subject is found to be unwell, they should be transported to the study site and an unscheduled visit conducted.

#### 6.3. Efficacy

#### 6.3.1. Parasitology

#### Asexual parasite counts:

Microscope blood slides will be prepared on day 0 at screening and pre-dose, then every 8-hours during the in-patient stay until discharge on day 3. Microscope blood slides will be prepared at each subsequent visit on days 7, 14, 28 and 42. At each timepoint two thick and one thin film should be prepared. See Study Reference Manual for staining and counting methodology.

At screening the subject's parasitaemia should be calculated against a nominal white blood cell count (WCC) of 8,000/ul, as the haematology result will not be available at this stage:

Screening parasitaemia /ul = (number of parasites / number of WBCs counted) x 8,000

The day 0 pre-dose parasitaemia should be calculated against the subject's day 0 WCC value to reflect the baseline parasitaemia, just prior to dosing. All subsequent parasitaemias should be calculated against the WCC for that visit e.g. on day 3:

d3 parasitaemia /ul = (number of parasites / number of WBCs counted) x d3 WCC

If the thick film contains >10 asexual parasites/ul, the thin film should be read and parasites counted against a minimum of 500 red blood cells. Parasitaemia from thin films is calculated as:

Parasitaemia/ul = (number of parasites / number of RBCs counted) x RBC count

The calculated parasitaemia/ul will be recorded into the eCRF for each timepoint. See the Study Reference Manual for quality control procedures.

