#### 6.3.5. Clearance times (PCT and FCT)

Subjects will also be assessed for these secondary endpoints against the following definitions:

- **PCT**: Time needed to clear asexual parasite forms from the blood, parasite numbers fall below the limit of detection in a thick blood smear and remain undetectable for at least 48 hours.
- **FCT:** Time from the first dose of treatment to the time when body temperature falls to normal and remains so for at least 48 hours.

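### Section 6.3.1 sends slides to a thin film at more than 10 parasites/ul, but at its 500 red-cell minimum the smallest non-zero result is several thousand/ul, and it does not say which value is recorded

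*Protocol*

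**What the plan says.** Protocol section 6.3.1 gives three instructions for asexual counts.

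- **Thick film, white-cell based.** At screening a nominal white-cell count is used because haematology is not yet available: "Screening parasitaemia /ul = (number of parasites / number of WBCs counted) x 8,000". The Day 0 pre-dose value uses the subject's own Day 0 white-cell count. All later values use the white-cell count for that visit, with Day 3 as the worked example.
- **Thin film, red-cell based.** "If the thick film contains >10 asexual parasites/ul, the thin film should be read", with "parasites counted against a minimum of 500 red blood cells", and "Parasitaemia/ul = (number of parasites / number of RBCs counted) x RBC count".
- **Recording.** "The calculated parasitaemia/ul will be recorded into the eCRF for each timepoint". No sentence says which value this is when both films have been read, or what to enter when the thin film shows no parasite.

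Counting detail is deferred: "See Study Reference Manual for staining and counting methodology". The red-cell count is one of the section 6.2.2 haematology tests ("red blood cell count, white blood cell count, platelet count").

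The endpoints use these counts in different ways. Two early-treatment-failure (ETF) criteria in section 6.3.4 compare densities: Day 2 above Day 0, and Day 3 at least 25% of Day 0. Section 3.2 lists density summaries over time as a secondary endpoint. Late clinical failure (LCF), late parasitological failure (LPF) and the Day 28 cure derivation in section 11.3.5.1 turn on whether parasites are present. Parasite clearance time (PCT) in section 6.3.5 is tied to the thick film: "parasite numbers fall below the limit of detection in a thick blood smear".

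**The concern.** A thin film read against a few hundred red cells suits heavy infections. Here it is called for at a density where 500 red cells will almost never contain a parasite. The trigger and the cell count therefore do not fit together, and the unit or the level of the trigger looks wrong.

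The section also contradicts itself in two places:

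- Every later density is to use the visit white-cell count, yet the red-cell formula is invoked for almost every positive slide.
- Haematology is said to be unavailable at screening, yet any screening slide that meets the 2,000/ul entry limit exceeds 10/ul and so calls for a formula that needs the red-cell count.

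At stake are the density-over-time endpoint and the two ETF comparisons with Day 0. ETF enters the adequate clinical and parasitological response endpoint, and under section 6.3.4 it leads to rescue medication. There is also an open question for cure: section 11.3.5.1 assigns failure programmatically from positive counts, so it matters which count is in the eCRF.

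**Working it through.** The plan derives no figure from the trigger or the cell count, so there is none to reproduce.

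**Inputs.** From section 6.3.1: trigger 10/ul, minimum 500 red cells, and the formulas. From section 5.2.1: entry density from 2,000/ul. Assumed, because the protocol gives no value: a red-cell count R of 4 million/ul, range 3 to 5 million/ul.

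**Step size.** One parasite in 500 red cells equals R/500:

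- 3,000,000/500 = 6,000/ul
- 4,000,000/500 = 8,000/ul
- 5,000,000/500 = 10,000/ul

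Against the trigger this is 6,000/10 = 600 to 10,000/10 = 1,000 times. Against the entry limit it is 6,000/2,000 = 3 to 10,000/2,000 = 5 times.

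**Chance of seeing no parasite.** With true density D, the number seen is taken as Poisson with mean 500 × D/R, so P(zero) = exp(-500D/R).

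| True density (/ul) | R = 3 million | R = 4 million | R = 5 million |
|---|---|---|---|
| 11 | 99.8% | 99.9% | 99.9% |
| 500 | 92.0% | 93.9% | 95.1% |
| 1,000 | 84.6% | 88.2% | 90.5% |
| 2,000 | 71.7% | 77.9% | 81.9% |
| 5,000 | 43.5% | 53.5% | 60.7% |
| 10,000 | 18.9% | 28.7% | 36.8% |

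P(zero) drops below 50% at D = ln(2) × R/500, about 4,200 to 6,900/ul. It drops below 5% at D = -ln(0.05) × R/500, about 18,000 to 30,000/ul. To see one parasite on average at 10/ul, R/10 = 300,000 to 500,000 red cells would have to be read.

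**How often the trigger fires.** The lowest non-zero thick-film density is the white-cell count divided by the white cells counted. With the nominal 8,000/ul this is 8,000/200 = 40/ul, 8,000/500 = 16/ul or 8,000/800 = 10/ul. The protocol does not state the number counted for asexual forms. With fewer than 800 counted, every positive thick film exceeds 10/ul.

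**Effect on the Day 3 ETF rule if thin-film values are used on both days** (R = 4 million, 500 cells; rule taken as a positive Day 3 count of at least 25% of the Day 0 count).

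- True Day 0 20,000/ul (mean 500 × 20,000/4,000,000 = 2.5) and true Day 3 2,000/ul (mean 0.25), a true ratio of 10%. With one parasite on Day 3 the rule needs at most 4 on Day 0: 0.195 × 0.891 = 0.174. With two it needs at most 8: 0.024 × 0.999 = 0.024. Three or more add 0.002. The total is about 20%, so the rule is falsely met one time in five.
- Same Day 0 and true Day 3 6,000/ul (mean 0.75), a true ratio of 30%. The terms are 0.354 × 0.891 = 0.316, 0.133 × 0.999 = 0.133 and 0.041, in total about 49%. The rule is missed about half the time.
- The Day 0 count itself is zero with probability exp(-2.5) = 8% at 20,000/ul and 72-82% at the entry limit, which leaves no denominator.

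**The case against.** The strongest reply is that section 6.3.1 only says the thin film should be read. It does not say that the thin-film value replaces the thick-film value. It expressly prescribes white-cell-based densities for Day 0 and Day 3, the two days in the 25% rule. The figure of 500 is a minimum, and the Study Reference Manual, which is not available here, may require more cells or settle which value is recorded. The method is the same in both blinded arms, section 11.3.3.2 describes secondary comparisons as descriptive, and at high density the thin film performs better (coefficient of variation 17-22% at 200,000/ul).

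Much of this stands, and it limits two stronger readings that a reader might infer.

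- **That the cure, LCF, LPF and PCT results are corrupted.** The documents do not support this. Cure, LCF and LPF rest on presence of parasites, and a slide that triggers a thin-film read is already positive. PCT is defined on the thick smear. Harm arises only if a thin-film zero overwrites the positive thick film. The text does not require that, but it does not prevent it either. The filter papers taken from day 7 onward are not a full safeguard, because section 11.3.5.1 sends samples with positive counts for PCR.
- **That most positive follow-up slides would read zero.** This needs the distribution of densities at recurrence, which the protocol does not give. Zero is the more likely thin-film result only below about 4,200 to 6,900/ul.

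The reply does not remove the mismatch. Trigger, cell minimum and formula are all stated in the protocol itself. The white-cell sentences leave two conflicting rules for the same slide. Reading somewhat more than 500 cells would not help near 10/ul, where hundreds of thousands are needed.

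**Conclusion.** The rule is wrong as written. At its stated minimum, the thin film cannot measure densities over most of the range in which section 6.3.1 calls for it: the smallest non-zero value is 6,000 to 10,000/ul against a trigger of 10/ul. The section also gives a conflicting white-cell rule and asks for a red-cell result at screening, when haematology is unavailable.

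If the thin-film value is the one recorded, the density summaries and the Day 2 and Day 3 comparisons with Day 0 are unreliable, with errors of the order shown above. For cure, LCF and LPF the finding is an unclosed ambiguity and not a demonstrated error.

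The sizes rest on an assumed 3 to 5 million red cells/ul, exactly 500 cells read, and Poisson counts. The ETF illustration also assumes thin-film values on both days.

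**What to change.** In section 6.3.1:

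1. Reconcile the unit or level of the trigger with the red-cell count, so that the thin film is used only at densities where it yields an adequate number of parasites. The density giving k expected parasites in 500 cells is k × R/500; as an illustration, k = 10 at 4 million/ul corresponds to 80,000/ul. Keep the thick-film, white-cell-based density otherwise.
2. State which value is entered in the eCRF when both films are read, and which count or formula applies at screening.
3. State that positive or negative status for cure, ETF, LCF, LPF and PCT comes from the thick film, whatever the thin film shows.
4. Align the Study Reference Manual, and confirm which value sites have been instructed to enter.

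The cost is a few sentences and a check of the manual. No new slides or staff are needed, since thick and thin films are already prepared at every timepoint, and fewer thin films would have to be read.

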#### Gametocyte counts:

Thick film slides will be read for gametocytes on day 0 (screening and pre-dose), 1, 2, 3, 7, 14, 28 and 42. If gametocytes are present, they will be counted against a minimum of 200 WBCs and their density calculated as:

Gametocytes /ul = (number of gametocytes / number of WBCs counted) x WCC

#### 6.3.2. Parasite DNA analysis

Two drops of peripheral blood will be collected onto pre-printed filter papers, for subsequent DNA extraction and PCR analysis of *P.falciparum* DNA, on all subjects at screening and any day on or after day 7 when a blood slide is prepared.

PCR of the *P.falciparum* genes MSP-1, MSP-2 and GLURP will be used to distinguish between the initial infection reappearing (recrudescence or inadequate therapy received) and a new infection occurring on any day on or after day 7 in the 42-day follow-up period.

Resistance marker work will investigate the presence of mutations associated with resistance of anti-folate drugs in the genes encoding DHFR and DHPS [Kublin, 2002] and resistance to lumefantrine, *Pf*mdr gene, as below. DNA extraction from the dried filter-paper blood spots and mutation-specific nested PCR and /or restriction digestions to detect these mutations will be performed at a single laboratory, see Study Reference Manual for further details.

DHFR codons 51, 59, 108 and 164; DHPS codons 437, 540, 581 and 613; *Pf*mdr186N

#### 6.3.3. Parasitological Cure Rate

Whether a subject has achieved the primary endpoint of parasitological cure rate will be determined based on the parasitology data with PCR correction for re-infection / recrudescence as described above on day 28, and on day 14 and 42 for the secondary endpoint analysis. If a subject has a recrudescence of the initial infection, or the PCR result is inconclusive, they will be categorized as a failure. Subjects without parasitology data on day 14, 28 or 42 will be considered not assessable for that timepoint.

#### 6.3.4. Adequate Clinical and Parasitological Response

Subjects will also be assessed for this secondary endpoint against the following definitions and described as either having an Adequate Clinical Parasitological Response (ACPR), early treatment failure, late parasitological failure, late clinical failure, or being not assessable, on Days 14, 28 and 42

#### **Early Treatment Failure (ETF):**

- Development of danger signs or severe malaria on Day 1, 2 or 3 (as defined in World Health Organisation. Severe falciparum malaria. *Trans R Soc Trop Med Hyg*, 2000; 94, supplement 1, [World Health Organisation, 2000]) in the presence of parasitaemia
- Parasitaemia on Day 2 higher than Day 0 count, irrespective of tympanic temperature
- Parasitaemia on Day 3 with tympanic temperature  $\geq 38.0^{\circ}$ C
- Parasitaemia on Day  $3 \ge 25\%$  of count on Day 0

#### Late Clinical Failure (LCF):

- Development of danger signs or severe malaria after Day 3 in the presence of parasitaemia, without previously meeting any of the criteria of ETF
- Presence of parasitaemia and tympanic temperature ≥ 38.0°C (or history of fever) on any day from Day 4 to Day 28, without previously meeting any of the criteria of ETF

#### Late Parasitological Failure (LPF):

• Presence of parasitaemia on any day from Day 7 to Day 28 and tympanic temperature < 38.0°C, without previously meeting any of the criteria of ETF or LCF

#### Adequate Clinical and Parasitological Response (ACPR):

• Absence of parasitaemia on Day 28 irrespective of tympanic temperature without previously meeting any of the criteria of ETF, LCF or LPF

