#### Secondary endpoints:

- Parasitological cure rate, PCR-corrected, at day 14 and 42.
- ACPR, and ACPR PCR corrected at day 14, 28 and 42.
- Summary of asexual parasite densities on days 0, 1, 2, 3, 7, 14, 28 and 42 by treatment group.
- PCT and FCT by treatment group.
- Summary of gametocyte densities on days 0, 1, 2, 3, 7, 14, 28 and 42 by treatment group.
- Safety assessments, including AE and SAE reporting, laboratory results and Glucose-6-phosphate-dehydrogenase (G6PD) status.
- Population PK parameters.

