## 3.2. Secondary

#### Secondary Efficacy Endpoints:

- Parasitological cure rate, PCR-corrected, at day 14 and 42, by treatment group.
- ACPR, and ACPR PCR corrected at day 14, 28 and 42, by treatment group.
- Summary of asexual parasite densities on days 0, 1, 2, 3, 7, 14, 28 and 42 by treatment group.
- PCT by treatment group.
- FCT by treatment group.
- Summary of gametocyte densities on days 0, 1, 2, 3, 7, 14, 28 and 42 by treatment group.

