# 11.3.5. Key Elements of Analysis Plan

# 11.3.5.1. Data derivation

For the primary endpoint, Parasitological Cure Rate at Day 28, in order to be classified as 'cured' at Day 28, subjects must demonstrate parasite clearance of their initial infection either at day 7 (+/- 1 day) if tested at this time point, or earlier (during day 3 to 6) if not tested at day 7, and must remain clear of their initial infection at day 28 (- 1, +3 days) following PCR-correction. These are the minimum data points required for a subject to be included in the primary analysis.

If a positive parasite count is detected at any intermittent timepoint day 7 to day 28, the patient will be programmatically classified as a 'failure'.

However, PCR analysis will be conducted on samples with positive counts at any intermittent timepoint day 7 to day 28 to assess if the parasites represent a recrudescence (re-infestation of the original baseline parasite infection) or a re-infection (infection with a new parasite after the baseline assessment). If a positive parasite count is determined to be a re-infection then the data for this subject will not be included as a 'failure' but rather will be excluded from the analysis since a new infection does not demonstrate a failure to treat the original infection.

Similarly, for the Day 14 analyses, patients must have data at either day 7 (+/-1 day) if tested at this timepoint or earlier (day 3 to 6) if not tested at day 7, and must remain clear of their initial infection at day 14 (-1,+3days) following PCR-correction. These are the minimum data points required for a subject to be classified as a responder in the Day 14 analyses. The Day 42 analysis would require the same timepoints; however, instead of Day 14 (-1,+3 days), Day 42 (-1,+3 days) would be required.

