# 11.3.5.7. Efficacy Analyses

The primary analysis is the Per Protocol analysis of the Parasitolgical Cure Rate (PCR-corrected) at Day 28.

A key supportive analysis will be the Intent-to-Treat analysis of the Parasitological Cure Rate (PCR-corrected) at Day 28, with missing data imputed as treatment failure

Additional sensitivity analyses of the primary endpoint will be performed to assess the robustness of the primary analysis to modifications in assumptions and methods. Analyses such as the following will be performed:

- Intent-to-Treat analysis of the Parasitological Cure Rate (PCR-corrected) at Day 28, with missing data excluded.
- Per Protocol analysis of the Parasitological Cure Rate (without PCR correction) at Day 28.

Secondary Analyses will include:

- Parasitological cure rate of CDA vs artemether-lumefantrine at day 14 (PCR corrected).
- Parasitological cure rate of CDA vs artemether-lumefantrine at day 42 (PCR corrected).
- Adequate Clinical and Parasitological Response rate (ACPR [World Health Organisation, 2003]) at day 14, 28 and 42 (all PCR corrected).
- Asexual parasite densities over time for CDA vs. artemether-lumefantrine.
- PCT of CDA vs artemether-lumefantrine.

- Gametocyte density over time of CDA vs artemether-lumefantrine.
- FCT of CDA vs artemether-lumefantrine.

Details of theses analyses will be documented in the Reporting and Analysis Plan (RAP).

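### ACPR is to be classified on Days 14, 28 and 42, but Protocol section 6.3.4 ties the febrile LCF, LPF and ACPR definitions to Day 28 only

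*Protocol*

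**What the plan says.** Section 6.3.4 places every child in one of five categories: ACPR, early treatment failure (ETF), "late parasitological failure, late clinical failure, or being not assessable, on Days 14, 28 and 42". The endpoint lists use the same three days. The Protocol Summary has "ACPR, and ACPR PCR corrected at day 14, 28 and 42", section 3.2 repeats this by treatment group, and section 11.3.5.7 plans "Adequate Clinical and Parasitological Response rate (ACPR [World Health Organisation, 2003]) at day 14, 28 and 42 (all PCR corrected".

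The definitions that follow in section 6.3.4 use other days:

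- Late clinical failure (LCF) has two criteria. The one for danger signs or severe malaria starts after Day 3 and has no end day. The one for parasitaemia with fever applies "on any day from Day 4 to Day 28, without previously meeting any of the criteria of ETF".
- Late parasitological failure (LPF) is "Presence of parasitaemia on any day from Day 7 to Day 28 and tympanic temperature" below 38.0°C.
- ACPR is "Absence of parasitaemia on Day 28 irrespective of tympanic temperature without previously meeting any of the criteria of ETF, LCF or LPF".

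None of these is restated for Day 14 or Day 42. Section 11.3.5.1 does change the day, but in its derivation of parasitological cure: "The Day 42 analysis would require the same timepoints; however, instead of Day 14 (-1,+3 days), Day 42 (-1,+3 days) would be required".

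**The concern.** A response reported for a named day should depend on what was seen up to that day. Here the day in the endpoint changes and the definition does not. At Day 42 the categories cannot register a first non-severe recurrence after Day 28. At Day 14 they need a slide taken two weeks later.

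Two secondary results are at stake. Day 42 ACPR could include children who are parasitaemic at that visit, and so disagree with Day 42 cure in the same child. Day 14 ACPR could lose children with a valid Day 14 slide. Section 3.2 lists six ACPR endpoints (three days, with and without PCR correction), and four of them (two days × two versions) carry a day that the definitions do not address.

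**Working it through.** The plan states no figure on this point, so the check is to apply the definitions to test children.

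**Which categories reach Day 42 (section 6.3.4)**

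| Category | Days covered | Reaches Day 42? |
|---|---|---|
| ETF | Days 1 to 3 | No |
| LCF, danger signs or severe malaria | After Day 3, open-ended | Yes |
| LCF, fever criterion | Day 4 to Day 28 | No |
| LPF | Day 7 to Day 28 | No |
| ACPR | Day 28 slide, no prior failure | No |

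**Child A: no earlier failure, negative Day 28 slide, parasitaemia on Day 42 without danger signs or severe malaria.**

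1. ETF: not met, because it ends on Day 3.
2. LCF, severe criterion: not met, by construction.
3. LCF, fever criterion: not met even at 38.0°C or above, because it ends on Day 28.
4. LPF: not met if afebrile, for the same reason.
5. ACPR: met. The Day 28 slide was clear and no failure criterion applies.

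So child A is ACPR at Day 42. If Day 42 is read into the ACPR line alone, child A is no longer ACPR, but still meets no failure criterion and fits no category. Neither reading works.

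**Child A after PCR.** Three other rules matter:

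- Section 11.3.5.8.2, on adverse events, treats PCR-confirmed recrudescences as failures in efficacy analyses, with no day limit.
- Section 11.3.5.2 removes PCR-confirmed new infections from ITT efficacy analyses. Section 11.3.1 makes ITT the population for secondary efficacy.
- Section 3.1 defines cure as staying free of the initial infection up to the assessment day, so a Day 42 recrudescence fails Day 42 cure.

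For PCR-corrected ACPR, then, a recrudescence in child A is ACPR under section 6.3.4 and a failure under section 11.3.5.8.2. If the second rule prevails, the child is a failure with no LCF or LPF label. A confirmed new infection leaves the ITT analysis. For uncorrected ACPR neither rule settles the matter and the literal result in step 5 stands.

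**Child B: negative on Days 7 and 14, then lost.** ACPR requires a clear slide on Day 28, and child B has none. Child B cannot be ACPR at Day 14 and is at best not assessable. Section 6.3.3 treats the same child differently for cure, where only missing parasitology at that timepoint makes a child not assessable.

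**Size.** Under the literal rule, uncorrected Day 42 ACPR exceeds a count anchored to Day 42 by the number of Day 28 responders whose first non-severe recurrence falls on Days 29 to 42. The Day 14 loss is the number of children like child B. The documents give neither number.

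**The case against.** The strongest reply is that other current text shows what was meant. Section 11.3.5.8.2 makes PCR-confirmed recrudescences efficacy failures, section 11.3.5.2 excludes PCR-confirmed new infections, and section 11.3.5.7 plans ACPR as PCR-corrected throughout. Section 11.3.5.3 also sets windows around Day 14 and Day 42 for the analyses at those days without limiting them to cure. Section 11.3.5.7 leaves details to the Reporting and Analysis Plan, and section 11.3.3.2 calls comparisons on secondary endpoints descriptive.

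Much of this stands. A reader might infer that a Day 42 recrudescence will be counted as a response in PCR-corrected ACPR. The documents do not support that, because section 11.3.5.8.2 says otherwise; what they show is a conflict between two rules. A reader might also infer that a child first positive on Day 28 will be recorded as LPF at Day 14. That would use a later slide for an earlier status. The wording fails to give a usable Day 14 rule, but it does not show that such children would be counted as failures there.

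The reply does not remove the contradiction. Section 11.3.5.3 refers back to section 11.3.5.1, which derives parasitological cure, and neither changes the LCF, LPF or ACPR definitions. The rule on recrudescence sits in the adverse event section and does not name ACPR. Uncorrected ACPR is still a listed endpoint. The Reporting and Analysis Plan can add detail, but Day 28 is written explicitly into three definitions in the protocol, so this is a stated rule that does not fit, not a detail left open.

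**Conclusion.** The point holds as an internal contradiction in a secondary endpoint. Uncorrected Day 42 ACPR, as defined, counts a first non-severe recurrence after Day 28 as a response. PCR-corrected Day 42 ACPR is governed by conflicting rules. Day 14 ACPR depends on a Day 28 slide.

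This rests on a literal reading of section 6.3.4; the sponsor probably meant each day to stand for itself. The number of children affected is unknown, and no rate should be attached to it. It would go too far to say that all four Day 14 and Day 42 ACPR endpoints will be miscounted, since the PCR rules limit the Day 42 problem and the Day 14 problem arises only where the Day 28 slide matters.

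The primary endpoint, Day 28 ACPR and Day 42 cure are unaffected, and late recrudescence remains visible in Day 42 cure. Treatment of malaria found at the Day 42 visit is secured separately by section 9.3. The correction is worth making, but it does not threaten the trial's main conclusion.

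**What to change.** In section 6.3.4, replace Day 28 with *the day of assessment (Day 14, 28 or 42)* in three places:

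- the end of the window in the LCF fever criterion, which then runs from Day 4 to the day of assessment;
- the end of the LPF window, which then runs from Day 7 to the day of assessment;
- the slide day in the ACPR definition.

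Child A then becomes LCF or LPF at Day 42 according to fever, before any PCR correction. Child B becomes ACPR at Day 14. Categories at Day 28 do not change.

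The cost is three phrases. Slides (section 6.3.1), temperatures (section 6.2.1) and filter papers for PCR (section 6.3.2) are already collected on Days 14, 28 and 42, so no new data are needed. If the protocol is not amended again, the change can be recorded in the Reporting and Analysis Plan before unblinding, as section 11.3.5.6 allows.
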